#### Overall Rationale for the Amendment:

This protocol is being amended to narrow the range of body weight in Cohort 3 in order to generate additional safety, tolerability, and PK data of tirzepatide in participants with relatively lower body weight. A lower limit was also selected for the body weight as a conservative approach, based on available adult exposure data from PK/PD modeling.

Section # and Name	Description of Change	Brief Rationale
Section 1.1 Synopsis – treatment arms and planned duration	Updated screening body weight for Cohort 3	Participants with body weight in the range of 40 to 60 kg inclusive will be enrolled in Cohort 3: 

• narrow body weight range is selected to generate additional safety, tolerability, and PK data of tirzepatide in participants with relatively lower body weight

• upper limit of 60 kg is selected to obtain data from participants in 50 to 60 kg range who will receive a starting dose of <del>CC1</del> mg tirzepatide in addition to data from Cohort 1 which includes participants <math>\geq 50</math> kg

• sentinel dosing in first <del>10</del> participants in the body weight range of 40 to 50kg

Section 1.2 Schema	Updated schema to reflect body weight range and sentinel dosing for Cohort 3	
Section 2.3 Benefit/Risk Assessment	Deleted the text on 'lower body weight' for participants in Cohort 3	
Section 4.1 Overall Design	Updated text to include body weight range for Cohort 3  Sentinel dosing will be used for <del>CC1</del> participants in the body weight range of 40 to 50 kg in Cohort 3	
Section 4.2 Scientific Rationale for	Modified text on rationale for sentinel dosing in Cohort 3	

Section # and Name	Description of Change	Brief Rationale
Study Design		
Section 4.3 Justification for Dose	Updated text on body weight range for Cohort 3	
Section 5.1 Inclusion Criteria	Updated text on screening body weight for Cohort 3	
Section 8.3 Adverse Events, Serious Adverse Events and Product Complaints	Replaced the text on 'SAEs and AE of special interest' with all adverse events	Accurately describes what is being done in the study

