	
Comments: Tirzepatide injection sites must be rotated along the 4 abdominal quadrants. Dosing may be performed by clinic staff during in-clinic visits. Self-administration by participant or parent or legal guardian is permitted after the investigator assessed them as being adequately trained. The dose increase will happen at the 5th dose as indicated in Figure GPHV.1.1
														
Tirzepatide sampling for pharmacokinetics (hrs)		12, 24		P		X: within 24 to 96 hrs postdose		P	X: within 120 to 168 hrs postdose		P	X	X	X	
	
Comments: Sampling time is relative to the latest dosing time. The actual date and time of the sampling and the most recent SC injection administered prior to collecting the sample must be recorded. Days 15, 36 and final follow-up or early discontinuation sample must be time-matched with immunogenicity sampling. No sample collection is needed if the participant discontinued before receiving tirzepatide. P = predose samples that should be collected within an hour prior to dosing.
														
Immunogenicity sampling		P	P					P					X	X	
	
Comments: Exact time of sampling must be recorded. Days 15, 36 and final follow-up or early discontinuation sample must be time-matched with pharmacokinetic sampling. No sample collection is needed if the participant discontinued before receiving tirzepatide. P = predose samples that should be collected within an hour prior to dosing.
														

Abbreviations: BMI = body mass index; CRF = case report form; ECG = electrocardiogram; hrs = hour; IBT = intensive behavioral therapy; I/E = inclusion and exclusion criteria; P = predose.

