## 2.3. Benefit/Risk Assessment

The risks of tirzepatide have been consistent with risks associated with other GLP-1 receptor agonists currently marketed. Potential risks include, but are not limited to, GI effects, acute pancreatitis (very rare), increases in heart rate, and hypoglycemic events (GLP-1 receptor agonist class effect).

No clinically significant safety or tolerability concerns have been identified during the clinical investigation of tirzepatide up to the single dose level of 5 mg or multiple weekly doses, when escalated up to 15 mg in adults. Based on this information, the highest starting dose of [REDACTED] mg and the highest dose of [REDACTED] mg tirzepatide to be administered in this study are reasonably anticipated to be tolerable in this group of pediatric participants with obesity.

Body weight is a known covariate affecting tirzepatide exposures based on population PK analysis in adult patients with T2DM. It is predicted that the exposure may be approximately 2-fold higher in the population with weight <50 kg compared to that in adults (weight  $\geq$ 50 kg); therefore, a more conservative initial starting dose of [REDACTED] mg will be adopted for participants in the lower body weight cohort (Cohort 2). This is a mitigation approach taken to reduce the risk of safety and tolerability issues before commencing another cohort of participants on an initial [REDACTED]-mg dose (Cohort 3).

Based on the known pharmacology of tirzepatide, participants with obesity may benefit from clinically meaningful weight reduction after 8 weeks of treatment. Potential risks, such as GI effects, acute pancreatitis, increases in heart rate, and hypoglycemic events, are consistent with the risks associated with currently available long-acting GLP-1R agonists in adults. These risks are clinically detectable and manageable and will be monitored throughout the study.

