Likewise, the dosing of Cohort 3 participants (body weight 40 to 60 kg inclusive) will proceed only after the satisfactory review of safety and tolerability data from at least [redacted] participants who received at least 5 treatment doses in Cohort 2 as shown in [Figure GPHV.1.1](#). PK samples will be collected, and exposure data for tirzepatide will be analyzed during the study to support dose-escalation decisions where possible. Sentinel dosing will be used for [redacted] participants in the specific body weight range of 40 to 50 kg in Cohort 3 [redacted]. If safety and tolerability after at least 1 week are acceptable in the [redacted] sentinel participants, as clinically assessed by the investigator, the remainder of the participants in Cohort 3 ([redacted] tirzepatide and [redacted] placebo) in the 40 to 60 kg range can be randomized and dosed.

A final follow-up visit will occur within 4 to 6 weeks after last treatment or at least 4 weeks but up to 6 weeks for participants who discontinued prematurely.

Starting at Visit 2 (baseline visit), all participants will be offered intensive behavioral therapy (IBT) sessions (Section [5.3.1](#)) which will continue through the study period and until the final follow up.

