### 4.2. Scientific Rationale for Study Design

This study is designed to assess the safety, tolerability, and PK profile of tirzepatide administered SC in participants aged 6 to 11 years with obesity.

The dose justification for tirzepatide is provided in Section [4.3](#).

The sample size is customary for Phase 1 studies evaluating safety, tolerability, and PK and is not powered on the basis of any a priori statistical hypothesis testing for efficacy. The rationale for the sample size is provided in Section 9.5.

Placebo is included as a control, in a blinded manner for investigators, site staff, and participants, to allow an unbiased assessment of the data generated, which will allow a more robust comparison of safety, tolerability, and PD data.

Sentinel dosing design will be used in Cohort 3 because this cohort has a higher starting dose compared to Cohort 2, while allowing participants with body weight below 50 kg. Cohort 1 will include participants  $\geq 50$  kg at a starting dose of CCI mg. Cohort 3 will include participants in the range of 40 to 60 kg at a starting dose of CCI mg. Hence, sentinel dosing will be used in █ participants in the body weight range of 40 to 50 kg in Cohort 3, as this weight range is not included in Cohort 1. Sentinel dosing design is included to assess the tolerability or safety profiles due to increased starting dose in participants with obesity receiving tirzepatide.

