### 6.5.1. Data Review during the Study

Data will be analyzed while the trial is ongoing. An assessment committee will not be formed. Safety data will be reviewed by sponsor on a regular basis while participants are enrolled in the study.

Two safety data reviews are planned to occur during the Study GPHV. Such an interim safety review will not be considered as formal interim analyses. This review will be used to support dose decisions for subsequent cohorts to be enrolled. The interim data reviews will include the following:

- *Cohort 1 safety and tolerability data review*- all available safety and tolerability data up to at least Day 36 from at least [redacted] participants with obesity in Cohort 1 who received and completed at least 5 weeks of treatment, and
- *Cohort 2 safety and tolerability data review*- all available safety and tolerability data up to at least Day 36 from at least [redacted] participants with obesity in Cohort 2 who received and

completed at least 5 weeks of treatment and all available safety and tolerability data from Cohort 1 participants.

At the time of safety reviews, any available PK data may also be reviewed by sponsor.

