7. TREATMENTS

The following is a list of the study treatment labels that will be used in the TFLs.

Cohort	Study Treatment Name	Treatment order in TFL
1	Placebo QW (BW \geq 50 kg)	1
	CCI [REDACTED] mg tirzepatide QW (BW \geq 50 kg)	2
2	Placebo QW (BW <50 kg)	3
	CCI [REDACTED] mg tirzepatide QW (BW <50 kg)	4
3	Placebo QW (BW 40 to 60 kg)	5
	CCI [REDACTED] mg tirzepatide QW (BW 40 to 60 kg)	6

Abbreviations: BW = body weight; QW = once weekly

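### No summary visible in the SAP separates Cohort 3 children below 50 kg, at the higher starting dose, from those of 50 to 60 kg; a descriptive split would be a cheap improvement

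*SAP*

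**What the plan says.** **Weight and dose.** The protocol divides children at 50 kg (synopsis, 2.1). On exposure, protocol 2.3 states: "It is predicted that the exposure may be approximately 2-fold higher in the population with weight <50 kg compared to that in adults". Cohort 1 is 50 kg and above, Cohort 2 is below 50 kg, and Cohort 3 is 40 to 60 kg inclusive, so Cohort 3 straddles the line.

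**Purpose of Cohort 3.** Amendment (e) narrowed its weight range "in order to generate additional safety, tolerability, and PK data of tirzepatide in participants with relatively lower body weight". The same amendment table describes the 50 to 60 kg children as supplying data on "tirzepatide in addition to data from Cohort 1 which includes participants" of 50 kg or more. Protocol 4.2 uses sentinel dosing in Cohort 3 "because this cohort has a higher starting dose compared to Cohort 2, while allowing participants with body weight below 50 kg".

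**Reporting.** SAP 7 has six treatment labels, and the only tirzepatide label for Cohort 3 is "mg tirzepatide QW (BW 40 to 60 kg". SAP 10.5.1 summarizes treatment-emergent adverse events (TEAEs) by treatment. SAP 10.3 gives Cmax and AUC0-tau by cohort and dose. SAP 10.4.2 builds its main PD comparisons on the SAP 7 labels.

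**PK sample size.** Protocol 9.5 states the minimum number for PK characterization per weight category, below 50 kg and 50 kg or more. SAP 8 states it per cohort.

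**ECG.** Protocol 9.3.3.2 includes ECG parameters among the safety parameters and says that continuous safety variables are summarized. The protocol synopsis and SAP 10.5.6 report ECG findings only as adverse events. SAP 12 records no change from the protocol.

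**The concern.** Safety and tolerability are the primary objective. Cohort 3 adds one thing that Cohorts 1 and 2 do not: the higher starting dose in children below 50 kg. The 50 to 60 kg children in Cohort 3 mainly extend what Cohort 1 already shows. If both are reported in one column, a higher event rate or higher exposure in the lighter children is averaged with the heavier children's results. A reader of the summary tables cannot then see it. The trial would hold the answer to its own question without a planned table that shows it.

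The ECG and sample-size differences raise a smaller issue: two pairs of statements that a programmer or CSR author could resolve in either direction, under a SAP that declares no changes.

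**Working it through.** The trial states no hypothesis, power or effect size for this question, so there is no plan figure to reproduce. The check is a cross-tabulation of the labels, followed by illustrations on stated assumptions.

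**1. Weight category by starting dose, tirzepatide arms.** Dose digits are blacked out. That Cohort 3 starts higher than Cohort 2 rests on protocol 4.2. That Cohorts 1 and 3 share a starting dose is inferred from the Amendment (e) table.

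| Combination | Where it occurs | Own column in SAP 7? |
|---|---|---|
| 50 kg or more, higher start | Cohort 1, part of Cohort 3 | Yes (Cohort 1) |
| Below 50 kg, lower start | Cohort 2 | Yes |
| Below 50 kg, higher start | Part of Cohort 3 only | No |

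So 2 of 3 combinations have a column.

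**2. Every grouping visible in the SAP.**

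| Output | Grouping | Isolates the third combination? |
|---|---|---|
| TEAEs (10.5.1) | SAP 7 labels | 0 of 6 labels |
| PK parameters (10.3) | Cohort and dose | No |
| PD, main model (10.4.2) | SAP 7 labels | 0 of 3 contrasts |
| PD, additional model | Dose across weights | No |
| PD, fallback | Pooled tirzepatide against pooled placebo | No |

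**3. How much could one column hide?** This cannot be computed: the counts are blacked out, and the documents fix no split within Cohort 3 beyond the sentinel participants. The following is illustration only. Let f be the assumed share of the Cohort 3 tirzepatide arm below 50 kg.

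Pooled event rate = f × p(below 50) + (1 − f) × p(50 or more):

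| Assumed rates, below 50 / 50 or more | f = 0.25 | f = 0.50 | f = 0.75 |
|---|---|---|---|
| 60% / 20% | 30% | 40% | 50% |
| 40% / 20% | 25% | 30% | 35% |
| 80% / 40% | 50% | 60% | 70% |

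For exposure, if the lighter children had twice that of the 50 to 60 kg children, the pooled geometric mean would be 2^f times the heavier children's level: 1.19, 1.41 and 1.68 for the same f. The factor 2 is an upper-end assumption. The protocol's prediction compares all children below 50 kg with adults; no figure is given for 40 to 50 kg against 50 to 60 kg.

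**4. How informative is a small split cell?** With m children and an assumed 20% event rate, the chance of at least one event is 1 − 0.8^m: 49% for m = 3, 74% for m = 6 and 93% for m = 12. A split cell can show a common event, but an empty cell would not be reassuring.

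**5. Secondary points.**
- *ECG.* The Schedule of Activities gives a completer 7 tracings: Visit 1, Visit 2 predose and 8 hours, and Visits 3, 7, 10 and 12. Of these, 5 follow the first dose. Protocol 9.3.3.2 implies summaries of the parameters; the synopsis and SAP 10.5.6 do not. The conflict is inside the protocol, and the SAP follows the synopsis.
- *Sample size.* Cohort 1 lies wholly at or above 50 kg and Cohort 2 wholly below. If the blacked-out minimum is the same number, a per-cohort minimum already meets the per-category one. No numerical consequence is shown, but the units differ and SAP 12 does not say so.

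**The case against.** The strongest reply is that the SAP reports Cohort 3 as the protocol defines it. Reporting by cohort and arm is normal for a sequential-cohort Phase 1 study, and no passage promises safety tables by weight within a cohort. Protocol 9.3.2.1 itself asks for PK by dose and cohort. All of that stands, which is why this is an improvement and not an error.

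A reader might draw four stronger conclusions that the documents do not support:

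- *That the information is lost.* SAP 10.1 lists all databased data. All AEs and AE discontinuations are listed, and so is body weight. SAP 3 and protocol 9.3.3.2 allow further analyses.
- *That PK below 50 kg goes uncharacterized.* The sponsor's PK/PD group runs a population model, and weight is a known covariate in adults. SAP 10.3 does not name a weight term, but such a model could use one without any column split.
- *That a 2-fold contrast is being masked.* Protocol 4.3 says up to 2-fold and gives the adult Phase 3 weight range as 43.1 to 227 kg, so most of the 40 to 50 kg band overlaps weights already studied in adults.
- *That these children go unwatched.* The sentinel rule reads "If safety and tolerability after at least 1 week are acceptable in the" sentinel group. On escalation, the schedule says "The dose increase will happen at the 5th dose as indicated in" the study figure. Protocol 6.5.1 adds "Two safety data reviews are planned to occur during the Study GPHV", covering Cohorts 1 and 2. These facts concern conduct, not the analysis tables. The two reviews support dose decisions for later cohorts, and no cohort follows Cohort 3. The sponsor reviews safety regularly, its team is unblinded (SAP 6), and the pause rules in protocol 6.5 apply.

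The table shells are not available, and part of the model text in SAP 10.4.2 is blacked out. A weight term or an existing split cannot be excluded.

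What remains is narrower: listings require a reader to rebuild the group by hand, and permission to add analyses is not a plan to do so.

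**Conclusion.** The point holds as a cheap, specific improvement. In the visible SAP text, no planned summary isolates children below 50 kg at the higher starting dose, although the protocol divides children at 50 kg, frames PK characterization by that cut (9.5) and justifies sentinel dosing by that combination (4.2). The amount of dilution is unknown, and the illustrations above depend wholly on assumed rates, shares and exposure ratios.

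The conclusion rests on two conditions: that Cohort 3 enrols children on both sides of 50 kg, as its range permits, and that the unseen shells and blacked-out text contain no split. It does not support saying that the SAP breaches the protocol on Cohort 3 or that a safety signal would be missed.

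The ECG conflict and the change of sample-size unit are real but minor. They make the declaration in SAP 12 inaccurate.

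**What to change.** 1. **Cohort 3 tirzepatide.** Add descriptive summaries of TEAEs, AE discontinuations, and population-PK AUC0-tau and Cmax, split by screening weight below 50 kg and 50 kg or more. State that 50.0 kg goes in the upper group, matching the Cohort 1 definition; this matters because 50.0 kg is eligible for both Cohorts 1 and 3. Split placebo only where counts allow. That makes 7 columns instead of 6, or 8 with placebo split. Read the tables next to the listings and without inference. If the shells already hold this split, say so in the SAP.
2. **ECG.** Reconcile the protocol synopsis, protocol 9.3.3.2 and SAP 10.5.6 in one direction: either summarize ECG parameters by treatment and time point, if the intervals are in the database, or remove them from 9.3.3.2.
3. **Sample size.** Align the unit in SAP 8 with protocol 9.5.
4. **SAP 12.** Replace the declaration of no changes with a record of how items 2 and 3 were resolved.

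The cost is a few tables on data already collected, plus wording. No visit, sample, eligibility rule or dose changes. The downside is small cells, so an absence of events in a split column must not be read as evidence of tolerability.

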8. SAMPLE SIZE JUSTIFICATION

Approximately CCI [REDACTED] participants may be enrolled. This will allow PK characterization in at least CCI [REDACTED] participants each, exposed to tirzepatide, for each of the 3 cohorts. Evaluable participants are participants who receive at least 1 dose of the study intervention and have at least 1 evaluable PK sample. The sample size is customary for Phase 1 studies evaluating safety, tolerability, and PK, and is not powered on the basis of any a priori statistical hypothesis testing for efficacy.

Participants who do not complete all the study procedures may be replaced to achieve the planned number of completers.

Note: Enrolled means a participant's parent or their legally acceptable representative's, agreement to participate in a clinical study following the completion of the informed consent process and assent where applicable and screening. Potential participants who are screened for the purpose of determining eligibility for the study, but do not participate in the study, are not considered enrolled. A participant will be considered as enrolled if the informed consent is not withdrawn prior to participating in any study activity after the screening visit.

9. DEFINITION OF ANALYSIS POPULATIONS

“Full analysis set” will consist of all enrolled participants. Participants will be included in the analyses according to the planned intervention.

The “Safety” population will consist of all participants who received at least 1 dose of tirzepatide or placebo. Participants will be analyzed according to the intervention they actually received.

The “Pharmacokinetic” population will consist of all participants who received at least 1 dose of tirzepatide and have evaluable PK data.

All protocol deviations that occur during the study will be considered for their severity/impact and will be taken into consideration when participants are assigned to analysis populations.

10. STATISTICAL METHODOLOGY

10.1 General

Data listings will be provided for all data that is databased. Summary statistics and statistical analysis will only be presented for data where detailed in this SAP. For continuous data, summary statistics will include the arithmetic mean, arithmetic standard deviation (SD), median, minimum, maximum and number of observations; for log-normal data (e.g. the PK parameters: AUCs and C_{max}) the geometric mean and geometric coefficient of variation (CV%) will also be presented. For categorical data, frequency count and percentages will be presented. Data listings will be provided for all participants up to the point of withdrawal from study, with any participants excluded from the relevant population highlighted. Summary statistics and statistical analyses will generally only be performed for participants included in the relevant analysis population. For the calculation of summary statistics and statistical analysis, unrounded data will be used.

For change from baseline summary statistics, each individual change from baseline will be calculated by subtracting the individual participant's baseline value from the value at that time point. The individual participants' change from baseline values will be used to calculate the summary statistics (arithmetic mean, arithmetic SD, median, minimum, maximum and number of observations) using a SAS procedure such as Proc Univariate.

Data analysis will be performed using SAS® Version 9.4 or greater.

10.2 Demographics and Participant Disposition

Participant disposition will be listed. The demographic variables age, sex, race, ethnicity, country of enrolment (if more than one), site ID (if more than one), body weight, height, body mass index and waist circumference will be summarized by treatment and listed. All other demographic variables will be listed only.

10.3 Pharmacokinetic Assessment

Pharmacokinetic analysis will be the responsibility of Lilly's PK/PD group. Tirzepatide concentration data will be analyzed using a population PK approach using nonlinear mixed-effects modelling techniques implemented on the NONMEM® software to determine the C_{max} and $AUC_{0-\tau}$ of tirzepatide by each cohort and dose.

Derivation of the PK parameters and TFL production will be the responsibility of Eli Lilly.

